8.1.12 First hospitalisation for infection (primary end point)

Site Principal Investigators will determine if participant have met the primary end point *i.e.*, the date participant was admitted to the hospital for infection as defined in **Section 5.2**. If this is not clear, they will defer to the Chief Investigator for a final opinion. Patients will then be reviewed for adverse event monitoring and concomitant medications recorded. A physical examination (including weight, blood pressure, heart rate, temperature and oxygen saturation) will be performed or the findings recorded from the medical records if the participant is admitted to a hospital other than their recruiting trial centre.

Results of the standard of care blood tests taken on admission will be documented in the CRF including haematology (full blood count), clotting (INR), biochemistry (sodium, potassium, urea, creatinine, albumin, bilirubin, aspartate transaminase, alanine transaminase, alkaline phosphatase and gamma-glutamyl transferase), glucose and C-reactive protein. Blood, urine, stool, sputum, skin and/or ascitic culture results, as applicable, will be documented in the CRF along with the report of a chest radiograph if performed. Liver disease severity score (MELD, Child Pugh, UKELD) will be measured at this timepoint. It is recommended to use the MELD Na (UNOS/OPTN) Score Calculator from MD Calc, linked here: MELD Na (UNOS/OPTN) (mdcalc.com).

For those participants with alcohol-related or MASLD-ALD cirrhosis, an AUDIT questionnaire will be completed which may be performed up to 14-days following discharge. This can be undertaken over the telephone if the admission is to a hospital other than the recruiting hospital. ³⁴ If an urinary ethyl glucuronide/ethyl sulphate test has been performed as part of the standard of care, the result will be recorded in the CRF.

8.1.13 Month 24 (+/- 14 days) Visit:

Trial participants will attend for one final visit for adverse event monitoring and recording of concomitant medications. A physical examination (including weight, blood pressure heart rate, temperature and oxygen saturation) will be performed. Any abnormal vital signs data, which is deemed clinically significant by the investigator, taking into account medical history and concomitant medications, will be reported as an Adverse Event (AE) and recorded on the Adverse Event Log. The non-clinically significant vital signs data will not be recorded on the database.

Bloods will be taken for haematology (full blood count), clotting (INR), biochemistry (sodium, potassium, urea, creatinine, albumin, bilirubin, aspartate transaminase, alanine transaminase, alkaline phosphatase and gamma-glutamyl transferase), glucose and C-reactive protein.

Blood will also be taken for HbA1c (for participants with diabetes only) and a lipid profile (total cholesterol, HDL cholesterol, LDL cholesterol and triglycerides) for participants with MASLD or MASLD-ALD Overlap cirrhosis only. Liver disease severity score (MELD, Child Pugh, UKELD) will be measured at this timepoint. It is recommended to use the MELD Na (UNOS/OPTN) Score Calculator from MD Calc, linked here: MELD Na (UNOS/OPTN) (mdcalc.com).

A final quality of life questionnaire (EQ-5D-5L) ³⁸, Hospital Anxiety and Depression Scale (HADS) questionnaire will also be completed and for those participants with alcohol-related or MASLD-ALD Overlap cirrhosis, an AUDIT questionnaire will be

NHS Foundation Trust

completed. ³³ If an urinary ethyl glucuronide/ethyl sulphate test has been performed as part of standard of care, the result will be recorded in the CRF.

8.2 Laboratory Tests

8.2.1 Standard of Care:

The following routine blood tests will be performed at baseline (day 0) and at 3, 6, 12 and 18 and 24-months. These will form part of the safety assessment and adverse event monitoring and are anticipated to be taken as part of routine clinical care assuming participants with cirrhosis will be seen at least every 6-months in the outpatient clinic. These tests will be performed by the local laboratory.

- Full Blood Count (FBC) to include haemoglobin, neutrophils, platelets, WBC (lymphocytes) and monocytes.
- International Normalised Ratio (INR)
- Sodium
- Potassium
- Urea
- Creatinine
- Albumin
- Aspartate transaminase (AST)
- Alanine transaminase (ALT)
- Alkaline phosphatase (ALP)
- Gamma-glutamyl transferase (GGT)
- Glucose
- C-Reactive Protein (CRP)
- Bilirubin
- * HbA1c
- ** Lipid profile (Total cholesterol, HDL cholesterol, LDL cholesterol and triglycerides)
- ***Urinary ethyl glucuronide/ethyl sulphate test if tested locally as part of standard of care routine.

*For participants with diabetes only

**For participants with MASLD or MASLD-ALD Overlap Cirrhosis only

***For participants with ALD or MASLD-ALD Overlap Cirrhosis only

8.2.2 Study-Specific Tests:

Centres will be supplied visit-specific blood, urine and faeces collection kits with detailed instructions on collection, processing, storage and shipping. Blood will be collected in the supplied BD vacutainer tubes, centrifuged within 1-hour and stored/biobanked at -80 °C until shipping to the central laboratory at the James Black Centre, King's College London. Urine and stool samples will be collected in sterile universal containers and stored at -80 °C until shipping to the central laboratory at the James Black Centre King's College London. Urine and stool samples will be collected in sterile universal containers and stored at -80 °C until shipping to the central laboratory at the James Black Centre, King's College London. Frequency for the collection of the samples will be decided by the Trial Manager after liaising with individual sites and will be dependent on the number of participants recruited per month per site. At the end of the trial, blood and surplus samples collected will be stored at the King's Liver Research Tissue Bank for use in future research programmes..

| Study-specific laboratory analyses | Baseline | Month 3 (+/- 14 days) | Month 6 (+/- 14 days) | 1 year (+/- 14 days) |
|---------------------------------------------------------------------------------------------------------------------------------------------------------------------------------------------------|----------|-----------------------|-----------------------|-----------------------------|
| Blood* (EDTA purple) 9mL x2 for bacterial DNA quantification and immunological marker assays | Х | X | х | X |
| Blood* (Clotted Gold) 5mL x1 for storage | Х | X | x | X |
| Blood* (Clotted red 9mL x2 for metabonomic profiling (serum) and bile acid profiling (LCMS) | Х | X | Х | X |
| London sites: Imperial, St. George's and King's College Hospital Blood* (Lithium heparinised green 9mL x8, for PBMC, monocyte phenotype and function assays and metabonomics (plasma) | Х | X | X | X |
| Non-London sites Blood* (Lithium heparinised green 9mL x1, for metabonomics (plasma)) | | | | |
| Urine for metabolic profiling (20 mL sterile universal container) (metabonomic analysis with LCMS) | Х | Х | Х | Х |
| Faeces for biomarker, metabonomic, proteomic and cytokine analysis (20 mL sterile stool collection container) | Х | X | х | Х |

Table 3: Summary of the study specific tests

| Faeces for metagenomic sequencing (20 mL sterile stool | Х | Х | Х | Х |
|---------------------------------------------------------------------------------------------------------------------|---|---|---|---|
| collection container) (microbiome composition including mycome and virome diversity, pathogenic species of interest | | | | |
| and resistome) | | | | |
| | | | | |

*To screen, we will look at SoC bloods no longer than 3 months. If it is older than 3 months, it will need to be updated.

9 Assessment of Efficacy

9.1 Efficacy Parameters

The following efficacy parameters will be recorded in the eCRF at the scheduled visits as per **Table 2**:

9.1.1 Primary Efficacy Parameters

To evaluate the efficacy of encapsulated FMT to reduce the susceptibility of infection in participants with cirrhosis measured by the time to first infection resulting in hospitalisation (primary endpoint).

9.1.2 Secondary Efficacy Parameters

- To evaluate the efficacy of encapsulated FMT to reduce **decompensating cirrhotic events**: (i) acute variceal bleeding, (ii) new onset ascites, (iii) spontaneous bacterial peritonitis, (iv) hepatic encephalopathy and (v) development of acute-on-chronic liver failure (the development of one or more organ failures). ³³
- To evaluate the impact of encapsulated FMT on all-cause hospitalisation documenting
 (i) length of stay and (ii) requirement for high dependency and intensive care.
- To assess the impact of encapsulated FMT on (i) antibiotic usage episodes and (ii) development of antimicrobial resistance as measured by colonisation with methicillinresistant Staphylococcus aureus (MRSA), vancomycin-resistant *Enterococci* (VRE), extended spectrum beta-lactamase producing bacteria (ESBL), linezolid-resistant *Enterococci* (LRE) and fluoroquinolone-resistant Gram negative and carbapenemresistant Enterobacterales (CRE). ⁸
- Change in liver disease severity scores (Child Pugh, ³⁹ MELD ²⁸ and UKELD ⁴⁰).
- All-cause and liver-related mortality.
- Change in **quality of life** (EQ-5D-5L questionnaire).
- Change in HADS score.
- Change in the alcohol-use disorders identification test (AUDIT score) ³³ and urinary ethyl glucuronide/ethyl sulphate levels recorded if tested as part of the standard of care in participants with alcohol-related or MASLD-ALD Overlap cirrhosis.

10 Assessment of Safety

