5.1 Trial Aims and Objectives

The aim of the PROMISE Trial will be to evaluate the efficacy and mechanisms of action of encapsulated FMT (*versus* placebo) to reduce infection and mortality in patients with alcohol-related (ALD) and Metabolic dysfunction-Associated Steatotic Liver Disease (MASLD) and MASLD-ALD Overlap cirrhosis. This approach has the added benefit that removing the possibility of endoscopy-related adverse events will reduce risk further.

The primary objective is:

1. To evaluate the efficacy of encapsulated FMT to reduce the susceptibility of infection in patients with cirrhosis measured by the time to first infection resulting in hospitalisation.

Secondary (clinical efficacy) objectives are as follows:

- 1. Evaluate the efficacy of encapsulated FMT to reduce decompensating cirrhotic events including acute variceal bleeding, new-onset ascites, spontaneous bacterial peritonitis, hepatic encephalopathy and progression to acute-on-chronic liver failure (ACLF).
- 2. To evaluate the impact of encapsulated FMT on patient outcomes including all-cause hospitalisation, disease progression, quality of life, mental health, alcohol use and survival.
- 3. To assess the impact of FMT on antibiotic usage and loss/reduction of antimicrobial resistance (AMR) genes.
- 4. To evaluate the safety of encapsulated FMT.

Following the assessment of efficacy, our **mechanistic aims are**:

- 1. To determine the mechanisms of action based on the hypothesis that the characteristics of the gut microbiome in cirrhosis drive the development of CAID.
- 2. To determine if FMT will favourably modify key contributors by improving gut microbiome diversity and reducing bacterial translocation into the systemic circulation.

The **mechanistic objectives** are:

- 1. Determine whether FMT increases the diversity of the gut microbiome in cirrhosis.
- 2. Determine whether FMT reduces bacterial translocation and endotoxemia.
- 3. Evaluate whether FMT improves CAID and reduces systemic inflammation.

The mechanistic objectives can be considered "exploratory" objectives and will not necessarily be covered in the primary paper.

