5.3 Secondary endpoints

- 1. Incidence of decompensating events including hepatic encephalopathy, new-onset ascites, variceal bleeding and spontaneous bacterial peritonitis over 24 month follow up period.
- 2. Progression to ACLF (the development of one or more organ failures). ³³
- 3. Infection rates and antibiotic usage following randomisation over 24 month follow up period.
- Incidence of AMR including skin and nose colonisation with methicillin-resistant Staphylococcus aureus (MRSA), vancomycin-resistant Enterococci (VRE), linezolidresistant Enterococci (LRE), extended-spectrum beta-lactamase producing bacteria (ESBL), fluoroquinolone-resistant Gram negative and carbapenem-resistant Enterobacterales (over 24 month follow up period).⁸
- 5. Hospitalisation rates (liver-related and all-cause) including the length of stay and admission to high dependency/intensive care (over 24 month follow up period).
- 6. Change in liver disease severity scores over 24 months post-randomisation (recorded every 3 months).
- 7. Change in quality of life (EQ-5D-5L score) at 3, 6, 12 and 24 months post-randomisation.
- 8. All-cause mortality, and liver-related mortality.
- 9. Change in depression and anxiety score using HADS at 3, 6, 12 and 24 months postrandomisation
- Change in alcohol use disorder-related events in patients enrolled with alcohol-related cirrhosis as assessed by the alcohol-use disorders identification test (AUDIT score) ³³ at 3, 6, 12 and 24 months post-randomisation, and urinary ethyl glucuronide/ethyl sulphate levels if tested as part of the standard of care.
- 11. Safety based on safety assessments including physical examination, clinical laboratory evaluation, vital signs and reported as adverse events (AEs) or serious adverse events (SAEs) over 24 month follow-up period.

Mechanistic endpoints:

- 1. **Matched faecal and plasma biomarkers** (D-lactate, fatty acid- binding protein 2 and ammonia) measured by enzyme-linked immunosorbent assay (ELISA).
- 2. **Faecal proteases** as markers of DNA replication, tissue re-modelling and immune response as a proxy of gut mucosal barrier integrity.
- Matched plasma and faecal cytokine profiles using a combination of ELISA and by electrochemiluminescence using the Mesoscale discovery platform (MSD) [Tumour necrosis factor-alpha, interferon-gamma, interleukin (IL)-1-beta, IL-6, IL-8, IL-10, IL-17A, IL-17E, IL-17F, IL-21 and IL-22].

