Trial participants must not have received antibiotics within 7-days prior to randomisation and at each dosing visit. The routine prescription of prophylactic antibiotics including ciprofloxacin and co-trimoxazole (prophylaxis of spontaneous bacterial peritonitis) and rifaximin (hepatic encephalopathy) will not be permitted at randomisation as they will reduce the efficacy of the FMT and will exclude a patient from the trial if the treating physician deems ongoing treatment is necessary. If at randomisation a participant is deemed likely to need to remain on the long-term antibiotics, then they should be excluded as this will impede the efficacy of the IMP. If any antibiotic is later clinically indicated during the course of the study for the treatment of suspected or confirmed infection, or rifaximin for the treatment of recurrent overt hepatic encephalopathy, then these will be permitted to be

given as standard of care. If the participant is receiving short term antibiotic treatment, there will be a 7-day washout period before continuing IMP per dosing schedule. If the participant is receiving long-term antibiotic treatment, the participant will continue to receive IMP as per the dosing schedule. The participant will no longer receive further IMP doses if they have been hospitalised for an infection and have met the primary endpoint.

The development of infection resulting in hospitalisation will meet the primary endpoint and the participant will no longer receive further IMP doses, although they will continue to be followed up for the duration of the trial.

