6.6 Concomitant Medication

Specific concomitant medications including antibiotics (as part of standard of care), beta blockers (Carvedilol and Propranolol), Lactulose (prebiotic), probiotics, anti-depressants/anti-anxiety/psychiatric medication and proton pump inhibitors (PPI) received during the treatment phase will be recorded in the relevant CRF for this trial.

Trial participant must not have received antibiotics within 7 days prior to randomisation and at each dosing visit.

The routine prescription of prophylactic antibiotics including ciprofloxacin and co-trimoxazole (prophylaxis of spontaneous bacterial peritonitis), rifaximin (hepatic encephalopathy) and probiotics (other than foods)* will not be permitted at randomisation as they may reduce the efficacy of FMT and will exclude a participant from the trial if the treating physician deems ongoing treatment is necessary. If any antibiotics is later indicated during the course of the study for the treatment of suspected or confirmed infection, or rifaximin for the treatment of recurrent overt hepatic encephalopathy, then these will be permitted to be given as standard of care.

If a participant has been treated with antibiotics for an acute infection following commencement of IMP which did not necessitate hospital admission *i.e.*, did not meet primary endpoint, then repeat dosing will be delayed until 7 days following finishing the antibiotic course. If, however the participant has been commenced on long-term prophylactic antibiotics as part of their standard clinical care that will continue for the remaining duration of the trial including ciprofloxacin and co-trimoxazole (prophylaxis of spontaneous bacterial peritonitis) and rifaximin (hepatic encephalopathy), then participants will be permitted to receive their IMP as per dosing schedule. If antibiotics are given during hospital admission due to infection then the participant has met the primary endpoint. This would result in discontinuation of IMP but the participant would remain in the study for follow-up.

Specifically, participants will not be required to follow a specific diet, nor will they be required to use contraception (FMT is not known to be teratogenic). Please refer to the Investigators Brochure for further safety data.

King's College Hospital

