10.1 Specification, Timing and Recording of Safety Parameters

The following safety parameters will be recorded in the eCRF at the scheduled visits as per **Table 2**:

- Adverse events (as detailed in 10.2)
- Episodes of infection not requiring hospital admission
- Antibiotic usage (number of episodes)
- Nausea for >72 hours following IMP administration.
- Abdominal pain or discomfort for >72 hours following IMP administration.
- Diarrhoea >7 days following IMP administration.

*Diarrhoea is defined in this study according to the World Health Organisation as the passage of three or more loose or liquid stools per day (or more frequent passage than is normal for the individual). Frequent passing of formed stools is not diarrhoea. If participants are taking lactulose or other aperients, these must have been stopped for 72-hours before diarrhoea can be diagnosed.

The following liver-related events, if leading to hospitalisation, will require expedited reporting to KHP-CTO:

- Liver disease progression
- Any known complication of cirrhosis including variceal bleeding, new-onset ascites, hepatic encephalopathy, spontaneous bacterial peritonitis, hepatorenal syndrome, acute-on-chronic liver failure and sepsis.
- Recurrence of ascites or jaundice
- Hepatocellular carcinoma
- Death as a result of a known complication of cirrhosis or disease progression.

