11.3 Analysis

Primary Outcome: The number of days from randomisation to first infection ³² leading to hospital admission.

Assessment of efficacy:

The main analysis will include all randomized participants (eligibility as defined in section 7) in the arms to which they were randomized, regardless of what treatment they received postrandomisation, with the intent to estimate an intention-to-treat (ITT) type estimand. For the primary analysis, a treatment policy strategy will be used for any intercurrent events (such as discontinuation of treatment or death), that is the occurrence of the intercurrent event will be considered irrelevant in defining the treatment effect of interest. Sensitivity analyses will examine this assumption using different strategies for the intercurrent events. Population definitions, target estimands and handling of intercurrent events will be further described in the Statistical Analysis Plan.

Primary analysis: A Cox baseline proportional hazards model of the time to infection will be fitted with frailty effect to account for site heterogeneity, adjusted for baseline disease severity, participant age, sex and baseline cirrhosis severity. The adjusted hazard ratio will be presented with associated 95% confidence interval. Proportionality will be assessed using a Kaplan Meier survival and log-log plots.

Secondary analysis:

Time to event outcomes including mortality (all-cause; liver-related), hospitalisation, progression to ACLF ³³ and hepatic decompensation will be analysed in a manner consistent with the primary analysis.

Binary outcomes (infection rates, AMR incidence and antibiotic usage) will be analysed with a mixed-effects multivariable logistic regression, fitting a random effect for site, and fixed effects for: participant age, sex, baseline disease severity.

Continuous outcomes (liver disease severity scores; AUDIT score; HADS score; EQ-5D-5L score) will be analysed using a mixed effects multivariable regression, adjusted in a consistent manner with the primary outcome analysis including baseline version of the outcome if applicable.

Missing data and population under investigation:

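### Antibiotic usage is measured in episodes and analysed as yes/no, so neither planned scale carries duration and a real difference in long-term antibiotic exposure can be strongly attenuated

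*Protocol*

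**What the plan says.** Secondary objective 3 in Protocol section 5.1 is "To assess the impact of FMT on antibiotic usage and loss/reduction of antimicrobial resistance (AMR) genes". The matching endpoint in section 5.3 gives a period but no unit: "Infection rates and antibiotic usage following randomisation over 24 month follow up period".

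The unit appears in two later places. Section 9.1.2 has "To assess the impact of encapsulated FMT on (i) antibiotic usage episodes", and the safety list in section 10.1 has "Antibiotic usage (number of episodes" (in brackets). Neither defines an episode.

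Section 11.3 then places the outcome on a third footing: "Binary outcomes (infection rates, AMR incidence and antibiotic usage) will be analysed with a mixed-effects multivariable logistic regression".

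The protocol expects courses of very different length after randomisation. For short courses, sections 6.2 and 6.6 (Concomitant Medication) delay the next dose by a 7-day washout. For long courses, section 6.2 says: "If the participant is receiving long-term antibiotic treatment, the participant will continue to receive IMP as per the dosing schedule". Section 6.6 describes participants "commenced on long-term prophylactic antibiotics as part of their standard clinical care that will continue for the remaining duration of the trial" and names ciprofloxacin, co-trimoxazole and rifaximin. No section makes duration or days of therapy an outcome.

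**The concern.** Objective 3 asks about antibiotic usage. The long-term part of that usage is what the protocol singles out. Section 4 worries that prolonged antibiotic prescribing drives resistance, and section 20 hopes FMT will reduce prophylactic use in particular.

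Long-term antibiotics are not permitted at randomisation, so every long-term start is a post-randomisation event that FMT could influence. The indications named, prophylaxis of bacterial peritonitis and recurrent encephalopathy, are themselves complications that FMT is hoped to reduce.

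A scale without duration gives such a start the same weight as a week of treatment. If FMT reduced long-term use, the planned summaries could show little of it, and objective 3 would be only partly answered.

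**Working it through.** The protocol states no rate, power or sample size for antibiotic usage, so there is no figure of its own to reproduce. The check is arithmetic on the three possible scales. All inputs below are assumptions unless marked otherwise.

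**Single participants.** A 365-day course and a 7-day course (365/7, about 52 times the exposure) each score 1 on the yes/no scale. Each also scores 1 episode if a continuous course counts once.

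**Episodes against days.** Let q be the proportion starting long-term antibiotics, L their mean length, s the number of seven-day courses per person, and r the share of short courses that long-term use prevents.

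- Episodes per person: E = q[1 + s(1 − r)] + (1 − q)s, which simplifies to s + q(1 − s·r).
- Days per person: D = q[L + 7s(1 − r)] + (1 − q)7s.

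Assume q = 0.25 (placebo) and 0.15 (FMT), L = 365, s = 1.5.

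| r | E placebo | E FMT | Episode ratio | D placebo | D FMT | Days ratio |
|---|---|---|---|---|---|---|
| 0 | 1.75 | 1.65 | 0.94 | 101.75 | 65.25 | 0.64 |
| 0.5 | 1.5625 | 1.5375 | 0.98 | 100.44 | 64.46 | 0.64 |
| 0.8 | 1.45 | 1.47 | 1.01 | 99.65 | 63.99 | 0.64 |

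With r = 0 and shorter long-term courses:

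- L = 180: days are 45 + 10.5 = 55.5 against 27 + 10.5 = 37.5, ratio 0.68.
- L = 90: days are 22.5 + 10.5 = 33 against 13.5 + 10.5 = 24, ratio 0.73.
- The episode ratio stays at 0.94 in both.

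The attenuation therefore does not depend on the 365-day figure. From the simplified form of E, the episode ratio passes 1 only when s·r > 1. Here that means r > 1/1.5 = 0.67. At r = 0.8 the excess is 1.4%.

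**The yes/no scale of section 11.3.** Per 100 participants, assume no overlap between long-term and short-course users, and one course each.

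- Placebo: 25 long (365 days) and 30 short. Any use 55%; days 25 × 365 + 30 × 7 = 9335.
- FMT, fewer long-term starts: 10 long and 45 short. Any use 55%; days 10 × 365 + 45 × 7 = 3965, a fall of 57.5%.
- FMT, same starts but 180 days each: 25 long and 30 short. Any use 55%; days 25 × 180 + 30 × 7 = 4710, a fall of 49.5%.

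In both FMT examples the yes/no outcome shows no difference at all.

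**The reverse case.** Take the first model with r = 0, leave long-term use at q = 0.25 in both arms, and let FMT halve short courses (s from 1.5 to 0.75).

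- Episodes go from 1.75 to 1.00, ratio 0.57.
- Days go from 101.75 to 91.25 + 5.25 = 96.5, ratio 0.95.

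Total days alone would nearly miss this effect, because 91.25 of 101.75 placebo days (90%) come from long-term courses.

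**The case against.** The best defence is that an episode count is a reasonable measure of treated acute infection, which is close to the trial's central hypothesis, and that total antibiotic-days has the mirror-image weakness just shown. This stands. It argues against replacing episodes with days, but not against reporting both and separating the two kinds of use.

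A second defence is that defining an episode and deriving durations are normal SAP content. That is partly right: a duration summary could be added there without contradicting the protocol. But sections 9.1.2, 10.1 and 11.3 do fix scales, those scales disagree with each other, and none carries duration. Whether dates are collected is a matter of data capture and cannot be mended at analysis.

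A third defence is that the inputs are assumed. This also stands. The 25% on prophylaxis in section 4 is a prevalence in cirrhosis generally. Patients needing ongoing prophylaxis or rifaximin are excluded at randomisation, so that figure does not support a 25% rate of new starts here.

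A reader might go further and infer that the plan would report the effect in the wrong direction, or that an episode is simply the wrong unit. The documents do not support either. Reversal in the episode count needs long-term antibiotics to prevent more than two-thirds of short courses in this model, and no section gives such a percentage. Section 11.3 does not plan a ratio of episode counts in any case. Nor do the documents say that long-term use is the main driver of resistance. Resistance is measured directly, by colonisation (section 9.1.2) and by the resistome (section 5.3), whatever unit is used for antibiotics.

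**Conclusion.** The point holds as a limitation of a secondary outcome that is cheap to remedy. As written, neither the episode count nor the binary analysis can distinguish a week of antibiotics from a course lasting the rest of follow-up. On the yes/no scale this is certain. For episodes it rests on the natural reading of an undefined term.

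The likely consequence is attenuation. A 36% fall in antibiotic-days (ratio 0.64) appears as a 6% fall in episodes (ratio 0.94) under the assumed inputs, and a fall of about half in days can leave any use unchanged. These sizes are illustrations, because the trial's own proportions and durations are unknown. The mismatch between sections 9.1.2 and 10.1 (episodes) and section 11.3 (binary) needs no assumption. The primary result and the sample size are unaffected.

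**What to change.** 1. In sections 9.1.2 and 10.1, keep the episode count, define an episode, and restrict the count to short therapeutic courses.
2. Report long-term prophylaxis and rifaximin separately by arm: the proportion starting, and days.
3. Add antibiotic-days per person-time as a co-reported measure, not as a replacement.
4. Confirm that the CRF captures antibiotic start and stop dates through month 24, including after IMP is stopped. Section 6.6 (Concomitant Medication) ties recording to the treatment phase, while section 8.1.13 records concomitant medications at month 24 and section 6.2 continues follow-up after IMP ends. The protocol does not say that dates are collected.
5. Reconcile sections 9.1.2 and 10.1 with the binary analysis in section 11.3, and name a model that suits each scale.

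The cost is wording, a check on date capture, one or two extra tables, and a model that copes with skewed days. Sites already need the end date of a short course to apply the 7-day washout, so the added burden should be small. The date check should come first, since missing dates may be hard to recover later.
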